1.2 SAMPLE SIZE DETERMINATION AND POWER CALCULATIONS

Aim 1

We calculate that the study will have an 80% or greater power to detect a significant difference in the proportion of HIV testing associated with the intervention arm, assuming a proportion self-testing in the control arm of 38% (observed data from SEARCH in fishermen) if the proportion testing in the intervention arm is 52% or greater (odds ratio of 1.8), calculated using an Intraclass Correlation Coefficient (ICC) of 0.15 (conservative based on SEARCH data), 70 clusters each in the intervention and control arms, average cluster size of 7 in both arms, and a type-1 error rate of 5%.^{125,126} Figure 2 shows statistical power and the range of detectable odds ratios over extremes of clustering effects.

Aim 2

For the Aim 2 combined primary outcome of successful linkage to ART or PrEP within 3 months of intervention start (+about 1 month), this study will have a 80% or greater power to detect a significant increase in successful linkage, assuming a proportion successfully linked at 3 months in the control arm of 24% (based on observed SEARCH trial linkage rates weighted for the number of eligible PrEP HIV-negative men and HIV-positive men not currently in HIV care) if the observed proportion in the intervention arm is 39% or greater (odds ratio of 2.0), using an ICC of 0.15, 70 clusters each in intervention and control arms, a cluster size of 7 in both arms, and a type-1 error rate of 5%. Statistical power for combined ART or PrEP

start is similar, with a reduction in anticipated eligible numbers per cluster reduced to 6 resulting in a small increase in the detectable odds ratio to 2.2 or greater. Power for a separate analysis of ART initiation alone is likely to be low given the small numbers of new HIV infections in the study sample with odds ratios in excess of three or four required.

Aim 3

For the primary outcome, we will have \geq 80% power to detect a significant increase in viral suppression and adherence in those on ART and PrEP, respectively, assuming a proportion of successes in the control arm of 70% or greater power (*based on SEARCH trial data on viral suppression rates among fishermen and projected urine TFV detection rates of 70%, weighted for the likely number of men on PrEP (n=168) and men on ART (n=72)*). We assume the observed proportion of successes in the intervention arm will be 89% or greater using an ICC of 0.10, a design effect from clustering of 1.7, and a type-1 error rate of 5%. For the combined primary outcome of retention on ART or PrEP at 6 months (+ about 1 month), this study will have 81% or greater power to detect a significant increase in linkage assuming a proportion retained in care in control arm of 81% (*based on SEARCH data on retention rates weighted for the likely number of men on PrEP (n=168) and ART (n=72)*) if the observed proportion in intervention arm is 96% or greater using the above assumptions.

1.3 STATISTICAL ANALYSES

1.3.1 GENERAL APPROACH

As a general approach, we will use methods designed for the analysis of clustered data, given the inherent clustered nature of the intervention design. For the primary outcome we will utilize cluster adjusted Pearson's Chi-square tests comparing the proportion of study participants' HIV testing in the intervention versus the control arm and apply the analysis method in the same way for secondary analyses of linkage to HIV care and PrEP. In additional secondary analyses, we will use multilevel mixed-effects logistic regression with cluster-adjusted standard errors using cluster levels at the close social network and beach levels and allowing for random effects at the cluster and beach levels.

1.3.2 ANALYSIS OF THE PRIMARY ENDPOINT(S)

Primary Outcome: The primary outcome will be self-reported HIV testing in the past 3 months by participants, as measured in the 3-month follow-up surveys.

Primary Predictor: Cluster (social network) Randomized Arm (intent-to-treat), Intervention or Control.

Analytic Plan: For the test of the intervention effect on the primary outcome of self-reported HIV testing in past 3 months, we will utilize a cluster adjusted Pearson's Chi-square test comparing the proportion of subjects' HIV testing in the intervention versus the control arm. In secondary analysis, we will utilize multilevel mixed-effects logistic regression with cluster-adjusted standard errors and a binary outcome of reported HIV testing or not (including cluster as one of the levels with random effects allowed). We will

investigate factors that influence the probability of success of HIV testing, including characteristics of clusters (the close social networks' size and composition, metrics of connectedness, mean cluster self-testing rate), characteristics of the cluster's promoter (age, marital, HIV, ART, PrEP status, measures of the promoter's ties to close-social-network cluster members), and individual level characteristics (demographics, SES, prior HIV testing, duration in boat crew, self-reported HIV risk).

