6.5 RANDOMIZATION OF CLOSE SOCIAL NETWORKS

Close social networks will be randomized 1:1 to intervention and control arms using a computer algorithm

that performs randomization stratified by beach and network size in blocks of two networks. All network members will receive the study arm condition to which their network is assigned. Participation of all network members is not a requirement for network randomization.

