Analytic Plan: For the test of the *social network-central promoters and small incentive* intervention effect on the primary outcome of linkage to care or prevention within 3 months of intervention start we will utilize a cluster adjusted Pearson's Chi-square test comparing the proportion of subjects with documented linkage to care or prevention in the intervention versus the control arm. In secondary analysis, we will utilize multilevel mixed-effects logistic regression as described in Aim 1 to investigate factors that influence the probability of success of linkage to care and prevention. We will also evaluate the secondary outcomes of ART initiation among HIV-positive persons not currently on treatment, and initiation of PrEP among HIV-negative persons who screen as eligible. We will compare the initiation proportions between study arms using cluster adjusted Chi-square tests and additional multilevel mixed-effects logistic regression to identify influencing factors.

We will measure the combined outcome of 1) Proportion of HIV-positive participants with viral suppression (HIV RNA <400 c/mL) at 6 months missing=failure (unsuppressed) and 2) Proportion of participants adherent to PrEP (TFV levels of >=1500 ng/mL in urine indicating adequate adherence) at 6

months missing=failure (nonadherent). PrEP adherence will be measured at 6 and 12 months after initiation using our novel technology of *point-of-care rapid testing to assess TFV adherence in urine*). (+ about 1 month for all measures)

Secondary Outcomes: HIV testing uptake 3 to 6 months after intervention start and retention on ART at 6 months or PrEP at 6 months. Using clinic records, we will assess whether men had confirmatory HIV testing and those who initiated PrEP and ART attended scheduled appointments and record VL results. (+ about 1 month for all measures)

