#### 10) Randomization

The study will take place in Siaya county, which borders Lake Victoria and has a population of ~1 million. Its subcounties, Rarieda, Bondo, and Alego Usonga, have an estimated 79 beaches and nearly 38,000 fisherfolk. Its population relies heavily on fishing and subsistence farming, and has high rates of poverty. Siaya County is also burdened by high rates of HIV, tuberculosis and malaria. HIV prevalence is 19.5%, 28.9% in those aged 25-49 years, and highest among fisherfolk at 32.1%. High-risk behaviors, including concurrent partnerships, the "jaboya" sex-for-fish economy, and low condom use, enhance HIV risks.

To implement this study, trained RAs will conduct a census of selected beach communities in Siaya. In addition to the census, we will rely on the BMU registries to account for the

possibility that the census omits some fishermen. Using the social network data obtained from the census along with a name matching algorithm, we will identify close male social networks that exist in study communities. " close "networks will typically include 4-10 men. Their defining characteristic will be that individual members of any given network will be connected to each other on multiple domains that indicate strong ties between them. Following the identification of distinct close social networks in communities, we will analyze the network data to determine a *network-central man* having a high degree of connectedness across domains within each network. This man will be considered as the network-central 'promoter' of HIV testing and will be the main individual study staff will contact to implement intervention and control group activities and approached for consent. If a central man is not interested in participation, we will approach the next most central man. Local close networks with consenting promoters will be eligible for randomization.

Close social networks will be randomized 1:1 to intervention and control arms using a computer algorithm that performs randomization stratified by beach and network size in 8 blocks of 2 networks. All network members will receive the study arm condition to which their network is assigned. Participation of all network members is not a requirement for network randomization.

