### Section 4: Statistical Principles

### 16) Level of statistical significance:

Standard levels of significance testing will be used (p=0.05) for two sided-tests. We will report 95% confidence intervals and exact p-values (or p<0.001).

**17)** Description and rationale for any adjustment for multiplicity: (if so, detailing how the type I error is to be controlled.) Our primary outcomes were established in our protocol, and thus no adjustments will be made for multiplicity.

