## b. Secondary Outcomes:

- v. Retention on ART or PrEP at 6 and 12 months: Using clinic records, we will assess whether men who initiated PrEP and ART attended scheduled appointments, and will compare them to those who were either prescribed PrEP or tested positive for HIV.
- **27)** Analysis methods: Analysis methods to be used and how the treatment effects will be presented:
  - Aim 1: For the test of the intervention effect on the primary outcome of self-reported HIV testing in past 3 months, we will utilize a cluster adjusted Pearson's Chi-square test comparing the proportion of subjects self-testing in the intervention versus the control arm. In secondary analysis we will utilize multilevel mixed-effects logistic regression with cluster adjusted standard errors and a binary outcome of reported HIV self-testing or not (including cluster as one of the levels with random effects allowed). We will investigate factors that influence the probability of success of HIV self-testing, including characteristics of clusters (the close social networks' size and composition, metrics of connectedness, mean cluster self-testing rate), characteristics of the cluster's promoter (age, marital status, HIV status, ART/ PrEP status, measures of the promoter's ties to close-social-network cluster members), and individual level characteristics (demographics, SES, prior HIV testing, self-reported HIV risk, and other health behaviors and characteristics).
  - b. Aim 2: For the test of the social network-central promoters and small incentive intervention effect on the primary outcome of linkage to care or prevention within 3 months of intervention start we will utilize a cluster adjusted Pearson's Chi-square test comparing the proportion of subjects with documented linkage to care or prevention in the intervention versus the control arm. In secondary analysis we will utilize multilevel mixed-effects logistic regression as described in Aim 1 to investigate factors that influence the probability of success of linkage to care and prevention. We will also evaluate the secondary outcomes of ART initiation among HIV-positive persons not currently on treatment, and initiation of PrEP among HIV-negative persons who screen as eligible. We will compare the initiation proportions between study arms using cluster adjusted Chi-square tests and additional multilevel mixedeffects logistic regression to identify influencing factors.

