  - c. Aim 3: We will utilize a cluster adjusted Pearson's Chi-square test comparing the proportion of successes (HIV viral suppression and adequate TFV levels) among men (on ART and PrEP, respectively) in the intervention and control networks. For the outcome of retention on ART or PrEP at 12 months, we will utilize a cluster adjusted Pearson's Chi-square test comparing the proportion of subjects on ART or PrEP at 3 months post-trial start who are retained in care at 12 months in intervention versus control group. In secondary analysis we will utilize Cox proportional hazards regression to investigate factors that influence time to discontinuation of ART or PrEP based on clinic visits and chart abstraction. We will also use multilevel mixed-effects logistic regression to investigate factors that influence the probability of viral suppression and TFV detection in urine.
  - d. Any adjustment for covariates: Randomization should yield equivalence between arms on covariates, but if non-equivalence is found on baseline measures or from differential attrition, we will control for it by including the covariate in the model.
  - e. Methods used for assumptions to be checked for statistical methods: Distributional assumptions for outcome variables will be checked using descriptive statistics. For mediation models, the assumption of no interaction between exposure (i.e., intervention vs. control) and mediators will be checked using product terms. Transformations will be used for continuous outcome variables that are skew to obtain more symmetric distributions.
  - f. Any planned sensitivity analyses for each outcome, where applicable:

Not applicable.

g. Any planned subgroup analyses for each outcome including how subgroups are defined: NA

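### The primary tests for Aims 1 and 2 ignore the beach and network-size strata used to randomise the networks

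*Protocol*

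**What the plan says.** Protocol 6.5 describes 1:1 randomisation of networks by an algorithm "that performs randomization stratified by beach and network size in blocks of two networks". SAP section 10 names the same strata: "that performs randomization stratified by beach and network size in 8 blocks of 2 networks". Neither document defines the size groups.

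The primary tests carry no stratum term:

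- **Aim 1.** Protocol 1.3.2 specifies a cluster-adjusted Pearson "Chi-square test comparing the proportion of subjects" between arms, with randomised arm as the primary predictor. SAP section 27 has the corresponding "Chi-square test comparing the proportion of subjects self-testing in the intervention versus the control arm".
- **Aim 2.** Protocol 1.3.3 specifies a cluster-adjusted "Chi-square test comparing the proportion of subjects with documented linkage to care or prevention in the intervention versus the control arm", and SAP section 27 repeats it.

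The strata appear elsewhere only in part. Protocol 1.3.1 plans further secondary mixed models "allowing for random effects at the cluster and beach levels". The SAP's secondary model names the cluster as a level and does not mention beach. Both documents list network size among factors to explore. SAP section 27(d) says that "if non-equivalence is found on baseline measures or from differential attrition, we will control for it by including the covariate in the model". SAP section 16 states: "We will report 95% confidence intervals and exact p-values".

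**The concern.** Blocking within beach makes the two arms nearly equal in their mix of beaches, so differences between beaches largely cancel out of the arm comparison. An unstratified standard error still counts that between-beach variance as noise. The test then rejects too rarely under the null and gives up precision that the stratified design has already provided.

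The SAP's covariate rule does not repair this. It acts only on observed imbalance, and blocks of two within beach will normally keep beach balanced, so the rule would seldom select it. It also refers to a model, and the primary test is not one.

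There is indirect reason to expect beach differences. Sites are beaches paired with clinics (Protocol 3.1), two partner clinics offer 24-hour and weekend services (Protocol 7.3), and clinic location and hours are named as barriers (Protocol 4.2).

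Trial size matters because the current protocol is not settled on 70 networks per arm. It also states 80 networks in total (4.1, Study rationale), at least 45 promoters per arm (8.3), up to 45 per arm (4.1.2, Consent procedures) and at least 650 men (3.1; 2 × 45 × 7 = 630). The SAP's power section uses 40 networks of 8 per arm.

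**Working it through.** **Inputs from the documents.** ICC 0.15; two-sided 5% (SAP section 16); Aim 1 38% v 52%; Aim 2 24% v 39%; 70 networks of 7 per arm (Protocol 1.2) or 40 of 8 (SAP section 11); up to 10 beaches (Protocol 3.1).

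**The plan's own figure.** The design effect is 1 + (7 − 1) × 0.15 = 1.9, so the effective size per arm is 70 × 7 / 1.9 = 257.9. A two-proportion test then has 89.4% power for Aim 1 and 95.8% for Aim 2, so the stated 80% or more is met. With 45 × 7 the effective size is 315 / 1.9 = 165.8, giving 72.9% and 84.0%. With 40 × 8 it is 320 / 2.05 = 156.1, giving 70.2% and 81.7%. No stratum input is used.

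**Approximate size of the effect.** Let *s* be the share of between-network variance that lies between beaches (an assumption). At 7 men per network, the true variance of the arm difference relative to the unstratified estimate is

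(1.9 − 7 × 0.15 × *s*) / 1.9 = (1.9 − 1.05*s*) / 1.9.

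Type I error is 2 × [1 − Φ(1.96 / √ratio)].

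| *s* | variance ratio | type I error |
|---|---|---|
| 10% | 0.945 | 4.4% |
| 20% | 0.889 | 3.8% |
| 50% | 0.724 | 2.1% |

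**Simulation.** Logit-normal data were calibrated to ICC 0.15 at the control proportion. There were 10 beaches, networks of 4–10 men (mean 7) or 6–10 (mean 8), two size groups (an assumption), blocks of two within beach × size, and 8,000 trials per case. The unstratified test was the Donner–Klar adjusted chi-square. The stratified test was a linear model with arm, beach and size group, network-clustered leverage-corrected standard errors and a t reference.

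Unstratified type I error was 4.3–5.0% (*s* = 10%), 3.9–4.5% (20%) and 2.5–2.9% (50%). The stratified model ran at 4.5–5.6%.

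Power, unstratified → stratified:

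| Aim | Per arm | *s* = 20% | *s* = 50% |
|---|---|---|---|
| 1 | 70 × 7 | 88.9 → 90.8% | 91.1 → 95.2% |
| 1 | 45 × 7 | 72.0 → 74.5% | 74.9 → 83.4% |
| 1 | 40 × 8 | 70.1 → 72.8% | 72.0 → 81.5% |
| 2 | 70 × 7 | 95.2 → 95.8% | 96.3 → 98.5% |
| 2 | 45 × 7 | 82.0 → 83.9% | 84.2 → 90.6% |
| 2 | 40 × 8 | 80.7 → 82.7% | 83.0 → 90.0% |

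The standard error of the risk difference falls by about 5% at *s* = 20% and 14–15% at *s* = 50%. At *s* = 10% the power gain is 0.1–0.6 points. At *s* = 0 the strata cost 0.1–0.2 points at 70 × 7 and 0.9–1.9 points at the smaller sizes. With five beaches, unstratified type I error was 4.2–4.8% (20%) and 2.9–3.5% (50%), with similar power gains.

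**Robustness.**

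- The documents do not say which cluster adjustment is meant. An arm-only cluster-robust test gave type I error of 3.7–4.4% (20%) and 2.3–2.8% (50%), with power within 1.1 points of the chi-square.
- A simulation on the risk scale with 70 networks per arm gave Aim 1 type I error of 3.9% (*s* = 25%) and 2.3% (50%). Stratum effects brought these to 4.8% and 4.4%. Over all its null scenarios the stratified test ran at 4.4–6.1%.
- Another risk-scale simulation gave Aim 1 power of 88.9 → 91.0% at 70 × 7 (20%), 73.9 → 82.9% at 45 × 7 (50%) and 72.1 → 81.8% at 40 × 8 (50%), with a cost under 1 point at *s* = 0.

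**The case against.** The best reply is that nothing is broken. The test is valid, its error is in the safe direction, and 80% power holds in every 70 × 7 scenario. At a fixed total ICC the unstratified test's power does not fall as the beach share rises, so what is lost is an available gain and not power that the plan promised. That is correct.

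The size also rests on a figure the documents do not give. Large gains need a share near 50%, which at 38% testing implies a between-beach standard deviation of √(0.5 × 0.15 × 0.38 × 0.62) = 13 points, or beach rates from about 11% to 65% at ± 2 standard deviations. A 20% share implies about 8 points. The protocol calls its ICC conservative. At ICC 0.05 and a 20% share the variance ratio is (1.3 − 0.07) / 1.3 = 0.946, and type I error is about 4.4%. Study clinics are also to be chosen for participants' convenience, which may narrow beach differences. The 10–20% range is therefore the safer one to plan on.

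Two further replies are fair. Power of 70–75% at the smaller sizes is mainly a sample-size inconsistency, and at a 20% share stratifying does not restore 80% for Aim 1. A confidence interval can also be built from a cluster-adjusted variance without strata.

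None of this supplies a reason to leave the design strata out of the primary analysis. The beach random effect is in a secondary model only, and only in the protocol.

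**Conclusion.** The concern holds. The Aim 1 and Aim 2 primary tests do not reflect the stratified randomisation, and no other provision reliably brings beach in. The consequence is conservative inference and forgone precision, with no false-positive risk.

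At a 10–20% beach share the effect is small: unstratified type I error of 3.9–5.0%, and at most 2.7 points of power to gain. At 50% the gain is 2.2–4.1 points at 70 × 7 and 6.4–9.5 points at 45 × 7 or 40 × 8. There, stratifying takes Aim 1 from below 80% to above it.

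These figures rest on an assumed beach share, an ICC of 0.15, 10 beaches and two size groups. The direction follows from the design; the magnitude is uncertain.

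**What to change.** For Aims 1 and 2, name as primary a cluster-robust model for the risk difference with arm, beach and network-size group. Use network as the cluster, small-sample-corrected standard errors and a t reference. Take the p-value and the 95% confidence interval from that one model. Define the size groups. State that these prespecified strata, and not covariates picked on observed imbalance, define the primary estimate.

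A stratified, cluster-adjusted Mantel–Haenszel test is a simpler alternative but needs a small-sample correction. Uncorrected, it ran at 5.0–6.1% over beach and 5.4–6.6% over beach × size.

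The Aim 3 primary test has the same form. Stratifying it is optional, since no gain has been shown there.

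One minor clarification: any model reporting the arm effect should use baseline covariates only, so that the mean cluster self-testing rate listed in Protocol 1.3.2 and SAP section 27, if measured at 3 months, is not placed beside arm.

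The cost is wording in the SAP and protocol, to be settled before outcomes are analysed by arm. Both strata are known for every network at randomisation. The model uses about 10 degrees of freedom (9 for beach, 1 for size group). If beaches do not differ, it gives up about 0.2 points of power at 70 × 7 and up to 2 points at 45 × 7 or 40 × 8.

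### The Aim 1 secondary mixed model lists the network's own self-testing rate as an explanatory factor, which is circular under the SAP wording and partly circular under the Protocol wording

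*Protocol*

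**What the plan says.** Protocol 1.3.2 names the primary predictor as "Randomized Arm (intent-to-treat), Intervention or Control". It tests the intervention with a cluster-adjusted Pearson chi-square, which has no covariates. It then continues: "In secondary analysis, we will utilize multilevel mixed-effects logistic regression with cluster-adjusted standard errors", with "a binary outcome of reported HIV testing or not". The next sentence says the team will "investigate factors that influence the probability of success of HIV testing, including characteristics of clusters". The list of network characteristics includes "metrics of connectedness, mean cluster self-testing rate". Prior HIV testing appears separately, among the individual characteristics.

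SAP 27 (Aim 1) carries the same list, but its mixed model has "a binary outcome of reported HIV self-testing or not".

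Neither document gives a time point for the network rate or excludes a man's own result from it. Neither says whether the rate and study arm enter the same model.

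**The concern.** If the rate is taken at the 3-month visit, it is measured after the kits or vouchers went out, and it is computed from the answers it is meant to explain. In a network of 7, each man supplies 1/7 of his own predictor. Under the SAP wording, predictor and outcome are the same variable at two levels of aggregation.

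Two results are at stake. First, the stated purpose is to find factors that influence testing, and this term would appear as a very strong one whatever the truth. A reader would conclude that network norms drive testing. Second, if arm is in the same model, the rate lies on the path from arm to outcome, so the adjusted arm effect no longer estimates the effect of the intervention.

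**Working it through.** **Inputs.** Protocol 1.2 gives 70 networks per arm, mean size 7, ICC 0.15, 5% type I error, "assuming a proportion self-testing in the control arm of 38"%, and power of at least 80% "if the proportion testing in the intervention arm is 52% or greater (odds ratio of 1.8"). SAP 16 makes tests two-sided. SAP 10 gives typical network sizes of 4–10.

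**The plan's own figure.** Design effect = 1 + (7 − 1) × 0.15 = 1.9. Effective n per arm = 70 × 7 / 1.9 = 257.9. OR = (0.52/0.48)/(0.38/0.62) = 1.77, which rounds to 1.8. Null SE = √(2 × 0.45 × 0.55 / 257.9) = 0.0438. Alternative SE = √((0.38 × 0.62 + 0.52 × 0.48)/257.9) = 0.0434. Power = Φ((0.14 − 1.96 × 0.0438)/0.0434) = 89.4%. The stated floor of 80% holds, so the setting is a fair one for the check.

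**Algebra, SAP wording.** In a linear model y = a + b·arm + c·(network mean of y), the residuals y − ȳ sum to zero within every network. They are therefore orthogonal to any network-level variable, including arm. The least-squares solution is exactly b = 0 and c = 1, whatever the data, the number of networks or their sizes. A logistic model replaces the straight line with a similar S-curve, so the result is nearly the same.

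**Simulation.** There were 100 trials per scenario, with 70 networks per arm and sizes of 4–10 (fixed at 7 in the 38% v 52% scenario with 50/80 shares). Clustering was beta-binomial, and the model was a random-intercept logistic regression fitted by maximum likelihood. No beach-level effect was simulated. The Protocol rows need the share of testers who self-test, control/intervention. The documents give none, so these shares are assumptions.

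| True testing, ICC | Rate term in model | Arm OR | Arm p<0.05 | Rate term p<0.05 (median z) |
|---|---|---|---|---|
| 38% v 52%, 0.15 | none | 1.93–2.02 | 88–92% | – |
| 38% v 52%, 0.15 | SAP: mean of the outcome | 0.99–1.00 | 0% | 100% (about 14) |
| 45% v 45%, 0 | SAP: mean of the outcome | 1.00 | 0% | 100% (11.0) |
| 38% v 52%, 0.15 | Protocol, shares 60/60 | 1.30 | 44% | 100% (11.6) |
| 38% v 52%, 0.15 | Protocol, shares 50/80 | 0.64 | 80% | 100% (12.0) |
| 38% v 52%, 0.15 | Protocol, shares 30/90 | 0.31 | 100% | 100% (11.3) |
| 45% v 45%, 0 | Protocol, shares 50/80 | 0.61 | 99% | 100% (8.2) |

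The first row exceeds 1.77 because a random-intercept OR is conditional on the network. Under the SAP wording, single-trial arm log-ORs in the 38% v 52% scenarios ran only from about −0.11 to 0.13. The random-intercept SD fell from about 0.9 to 0.

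**Why the Protocol version can reverse sign.** The arm log-OR is roughly ln(1.77) = 0.57 minus the rate coefficient times the arm difference in self-testing rate.
- Shares 60/60: difference 0.312 − 0.228 = 0.084; 0.57 − 4.87 × 0.084 = 0.16, so the effect shrinks.
- Shares 50/80: difference 0.416 − 0.190 = 0.226; 0.57 − 4.87 × 0.226 = −0.53, so it reverses.
- Shares 30/90: difference 0.468 − 0.114 = 0.354; 0.57 − 5.05 × 0.354 = −1.22, so it reverses.

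This agrees in direction with the simulated log-ORs of 0.27, −0.44 and −1.16. Handing out kits raises the self-test share, so the term removes more than the intervention added.

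**Alternatives.** A follow-up mean that leaves out the man himself is not enough: with cluster-robust logistic regression the arm OR is still pulled down to 1.35 (log-OR 0.30). A pre-randomisation network rate, assumed to share each network's underlying propensity, keeps the arm log-OR at 0.65 (OR about 1.9), significant in 97% of trials.

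**The case against.** The strongest reply has five parts.

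- **One model is not stated.** The list sits in its own sentence about exploring factors, and SAP 27d has a separate rule for covariate adjustment, tied to baseline non-equivalence or differential attrition. That rule does not call for a follow-up self-testing rate. This stands: a reader might infer that the plan commits itself to reporting no adjusted intervention effect, but the documents do not say that. The arm result is conditional. The circularity of the term does not depend on it.
- **Timing is not stated.** The baseline survey collects testing history, so a baseline network rate could be meant. It is possible but less natural. Prior testing is listed separately at individual level, and Protocol 1.2 uses self-testing as a label for the trial outcome.
- **The Protocol's outcome is any testing.** A reader might infer that both documents regress the outcome on its own average and so force the arm effect to nothing. Read literally, only the SAP does so, and that SAP cites Protocol Version 4.0 while the current Protocol is Version 11.0. This stands as a limit on the claim. It does not make the Protocol wording safe, as the reversed estimates show.
- **The primary analysis is untouched.** Correct: the chi-square has no covariates. SAP 12 and 18 also promise differences between arms and confidence intervals, so the mixed model is not the only planned source of an estimate.
- **Deleting the term everywhere would cost something.** Aim 2 reuses the model for linkage, where a self-testing rate is not an average of the outcome and is a reasonable factor to explore. This stands and limits the fix.

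**Conclusion.** The point holds for the secondary Aim 1 mixed model, on the reading that the rate is measured at follow-up and includes the man's own result. Its apparent importance is then uninformative under either document's wording, with significance in 100% of simulated trials even with no clustering and no arm effect.

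The effect on the arm estimate needs one further assumption, that arm is in the same model. Under the SAP wording the arm OR then goes to about 1.00. Under the Protocol wording it is distorted by an amount, and possibly in a direction, that depends on the self-test share in each arm. The values 1.30, 0.64 and 0.31 illustrate assumed shares and are not predictions.

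The documents do not support a claim that the primary test is compromised or that a null intervention result is built into the plan. Severity is moderate, because this is a secondary analysis whose stated question would be answered wrongly.

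**What to change.** 1. In Protocol 1.3.2 and SAP 27 (Aim 1), remove the network self-testing rate from the testing models. Alternatively, replace it with the network's mean prior HIV testing from the baseline survey, excluding the man himself.
2. Add one sentence to both: no variable measured after intervention start enters a model from which an arm effect is reported. The baseline survey meets this rule. It follows randomisation (Protocol 8.4) but precedes promoter training and kit distribution (Protocol 8.5).
3. State one outcome, testing or self-testing, for the Aim 1 mixed model and use it in both documents.
4. The follow-up rate may stay in exploratory Aim 2 factor analyses that report no arm effect, with its time point stated.

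The cost is a few lines of text in each document. The replacement data are already collected, and neither the sample size nor the primary test changes.
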